The primary aim of this phase of the project is to execute a pilot feasibility trial to evaluate the preliminary efficacy of, usability of, and satisfaction with the VPMRC. A single treatment condition (Usual Care [UC] plus VPMRC) X two evaluation periods (baseline and 10 weeks post-baseline) design with multiple dependent measures will be employed. Participants in the study will be 55 Veterans with CLBP. Participants will continue to receive care as usual from their primary care providers (PCPs) and other healthcare providers.

Recruitment

VistA Search: We will identify potential Veterans for inclusion from available electronic medical record (EMR) data in VistA. All Veterans 18 years or older from VACHS (Station 689) with low back pain defined using the *International Classification of Diseases, Ninth Revision* diagnostic codes related to low back pain (724, 7240x, 7241x, 7242x, 7243x, 7244x, 7245x, 7246x, 7247x, 8460x, and 8472x) will be considered eligible. We will attempt to oversample OEF/OIF/OND, female, and minority Veterans, as these Veterans have high prevalence rates of chronic musculoskeletal pain conditions and are of particular interest in the context of the proposed study. We will then identify Veterans in this group to exclude psychiatric hospital admissions in the previous 30 days, suicide flag in the Electronic Medical Record (EMR), or behavioral alert flag in the EMR.

A letter will be sent to the identified Veterans from their PCPs informing them about the study and inviting them to participate. Veterans will be provided with information about the voluntary nature of the study and the option to "opt out" from further contact with study staff by notifying us of their lack of interest by phone, email or letter. Veterans who do not contact us will be called by the study RA to be further informed about the study and, if interested, to be screened for participation. Screening will include several of the key eligibility criteria for the study (e.g., confirmation of presence of CLBP, readiness to engage in self-management for pain, interest in Internet-based pain care, and absence of medical and psychiatric comorbidities). If screening suggests potential eligibility, and if the Veteran is interested, an in-person appointment for obtaining written informed consent and baseline assessment data will be scheduled. Solicitation letters will be mailed in waves in order to prevent overwhelming our capacity to offer participation in a timely manner.

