Interest in Internet-based pain self-management	X		
Can walk one block?	X		
Consent Form	X		
Chart/Medication Review	X		X
WHYMPI-Interference Scale	X		X
Numeric Rating Scale of Pain Intensity (0-10)	X		X
Profile of Mood States	X		X
Beck Depression Inventory	X		X
Multidimensional Fatigue Scale	X		X
MOS Sleep Scale	X		X
Behavioral Goal Adherence		X	X
Patient Treatment Satisfaction Scale			X
Treatment Credibility Scale			X
Module(s) completed		X	
Usability of Module		X	
Time and content accessed		X	
Post-intervention Measure			X

In addition to completing assessments at baseline and 10-weeks post-baseline, participants will be contacted by the study staff via telephone on a weekly basis beginning 1 week post-baseline and ending at 10 weeks post-baseline. The brief phone contacts will serve to confirm continued Internet access to the VPMRC and to remind participants to continue to complete the VPMRC modules. Qualitative and quantitative feedback will be obtained. Questions will be asked on the following dimensions: goal adherence for previous week's goals (using a 0-10 Likert scale, where 0 indicates no adherence to completing the goal and 10 indicates complete adherence), feedback regarding usability of the previous week's module(s), and specific indication of modules most recently completed. The study staff member will also solicit questions about the content of the VPMRC and provide clarifying answers to these questions. Strict limits will be placed on the nature of the responses and length of time of the calls (i.e., no greater than 10 minutes).

Intervention Description (UC+VPMRC)

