pain self-management skills. Participants will be encouraged to complete the skill modules at their own pace. Participants will also be able to access other modules not identified by the self-assessment if they are interested in completing them. Participants will be provided with a pedometer at the baseline assessment to facilitate completion of the exercise/walking module, which requires patients to track the number of steps walked each day.

Attrition

The RA and study coordinator will monitor the study for attrition and follow-up with participants when they appear at risk for withdrawal or report the intent to withdraw. If a participant contacts the study coordinator to withdraw, s/he will first ask if there is a problem that s/he can address that would allow them to stay in the study. If not, s/he will ask subjects who wish to withdraw from treatment if they will consider continuing to complete the follow-up assessments. To keep losses-to-follow-up at a minimum, every effort, including reminder e-mails and follow-up phone calls, will be made to collect post-baseline data. We will also prospectively collect the reasons for missing data such as "patient refusal due to difficulty completing skill modules" or "patient moved away". Reasons for missing data will be evaluated during data analysis.

Outcome Measures

Standardized and reliable interview and questionnaire measures will be used to assess outcome and process variables. These outcome measures are similar to those we have used in prior CBT efficacy studies and are consistent with CONSORT and IMMPACT guidelines. In addition to these outcomes we also propose to examine treatment satisfaction, treatment credibility, and goal accomplishment.

Primary Outcome:

Pain Interference: The 9-item Interference subscale of the West Haven-Yale Multidimensional Pain Inventory (WHYMPI) assesses pain-related interference in social, work and household functioning and has demonstrated good internal consistency (0.86) and stability (0.85 over 2 weeks).²⁸ The WHYMPI-Interference Scale was recommended by IMMPACT as a core outcome measure for this domain.²⁹ A reduction in WHYMPI-Interference Scale scores of 0.6 or greater has been identified as an indicator of meaningful improvement in physical functioning and will be employed in this study.³⁰

Secondary Outcomes:

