Pain intensity: Self-report of pain is recognized as the gold standard for pain assessment given the inherently subjective nature of pain. Although the numeric rating scale (NRS), verbal rating scale (VRS), and the visual analogue scale (VAS) are all reliable and valid measures of pain, there are differences that led to the IMMPACT recommendation and our selection of the NRS as the primary measure of pain. Of particular note is the fact that the NRS is the accepted measure for screening for the presence and intensity of pain for the VHA, and it is quite familiar to Veterans. Data from several studies suggest that use of this measure, relative to the VRS and VAS, yields fewer missing observations and is preferred by more participants, especially among older persons and among those prescribed opioids.³¹ The NRS can be easily administered by either a research assistant, via the telephone, or online as is proposed for this study. In this trial, participants will be asked, "Please rate your pain by indicating the number that best describes your average pain in the last 24 hours on a 0 (no pain) to 10 (pain as bad as you can imagine) scale".³² A clinically-meaningful reduction in pain intensity will be defined as a reduction in pain of 30% on the NRS relative to baseline NRS. This threshold is also consistent with IMMPACT recommendations based on an analysis of ten studies that examine changes in absolute ratings of pain intensity and independent ratings of treatment satisfaction.³³

Emotional functioning: Overall functioning will be assessed using the 65-item Profile of Mood States (POMS), a multidimensional measure of emotional functioning designed to assess six dimensions of mood and can be used in non-psychiatric or physically ill populations.³⁴ Internal consistency (0.84 to 0.95, depending on subscale) and test-retest reliability (0.65 to 0.74, depending on subscale) is good. Depressive symptom severity will be assessed using the 21-item Beck Depression Inventory (BDI) a widely used self-report measure with excellent internal consistency (.92) and stability (.80-.90).³⁵ Both measures were recommended by IMMPACT.²⁶

Fatigue: Clinical fatigue will be assessed using the Multidimensional Fatigue Inventory (MFI).³⁶ The MFI can be scored to produce 5 dimensions: general fatigue, physical fatigue, mental fatigue, reduced motivation, and reduced activity.

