Sleep Problems: Sleep problems will be assessed using the MOS Sleep Scale. The MOS is segregated into subscales addressing seven sleep domains (i.e. sleep disturbance, snoring, awaken short of breath or with headache, adequacy of sleep, somnolence, a problems index 1 and a problems index 2). An additional single item assesses quantity of sleep.³⁷

Behavioral Goal Adherence: Goal adherence for previous week's goals will be assessed via telephone on a weekly basis for 10 weeks post-baseline using a 0-10 Likert scale, where 0 indicates no adherence to completing the goal and 10 indicates complete adherence.

Tertiary outcomes:

Module completion: Participants will be asked during weekly (for 10 weeks) phone calls placed by the study staff about completion of modules (i.e., how many modules completed, which modules) during the previous week. In addition, the web developer will build a database to track time spent on each module, which modules were accessed, and number of times each participant accessed the program. This database will be linked only to userID and will not be linked with PHI.

Module usability: Participants will be asked during weekly phone calls about usability of modules. Specifically, they will be asked to rate each completed module on a 0-10 scale where 0= very difficult and 10=very easy, in terms of accessing information presented, understanding information presented, setting a module goal, navigating the module.

Treatment credibility: Participants' judgments of treatment credibility will be assessed at the post-baseline assessment interval using a questionnaire adapted from Borkovec and Nau.³⁸ This measure has been shown to have an internal consistency of .85 and test-retest reliability of .83.

Patient satisfaction: Patient satisfaction will be assessed by the Pain Treatment Satisfaction Scale which is a 5-item satisfaction survey designed to assess patient satisfaction with 5 domains of pain care.³⁹ This measure shows good internal consistency (.83-.90 across two samples) and significant associations to follow-up treatment satisfaction and staff and patient ratings of patient improvement.

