Because the primary and secondary hypotheses test differences in outcome measure scores across time, we will use paired t-tests, or their non-parametric analogs (e.g., Mann-Whitney test) to compare mean (or median) scores on the outcomes across time. Given the multiplicity of tests for secondary outcomes (i.e., six outcomes) and the power of the study, in addition to maximizing sample size, we will use the Bonferroni procedure p-value, which we conservatively estimate to be $p = 0.008$, based on an overall significance of $p = 0.05/6$, to account for the number of comparisons. Our six secondary outcomes will be examined with the purpose of informing future modifications to the VPMRC and additional hypothesis generation. We have not grouped within subsets in order to ensure a more conservative approach. Tertiary hypotheses will examine data related to usability (use of and functionality) and satisfaction (satisfaction, credibility) with the VPMRC and will be collected only at 10 weeks post-baseline. Descriptive statistics will be employed to examine these data in order to describe participants' experiences with the VPMRC.

As in Phase I, quantitative data from the Post-intervention Measure with added data from the weekly phone calls for Phase II regarding usability of and satisfaction with the VPMRC will be used to modify the program. In addition, we will use specific primary and secondary outcomes data to inform modification of the VPMRC. For instance, if the data suggest a significant reduction in pain interference, but more modest changes in fatigue or depression, specific modules, such as Pacing (the pleasant activity scheduling coping skill) or Adaptive Stress Response (the using positive coping statements coping skill) will be targeted for further content and presentation enhancement to increase benefit to patients on these important related outcomes. We will also use data from tertiary outcomes to further modify presentation of the various treatment modules. For example, if certain modules are clearly preferred, as indicated by participant report of modules completed and satisfaction with the modules, other, less-preferred modules may be further enhanced (e.g., changes to audio-visual aspects, presentation of content within modules) to increase use, interest, and satisfaction.

6. References:

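### The analytic plan names an independent-samples rank test (Mann-Whitney) as the fallback for a paired t-test in a one-arm, before-and-after design

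*Combined protocol and SAP*

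**What the plan says.** Under Phase II, Design, the trial is described as "A single treatment condition (Usual Care [UC] plus VPMRC) X two evaluation periods (baseline and 10 weeks post-baseline) design", with 55 participants. There is no comparison group.

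The Phase II part of the Analytic Plan says that the primary and secondary hypotheses concern change over time. It will compare mean or median scores using "paired t-tests, or their non-parametric analogs (e.g., Mann-Whitney test". It does not say what would trigger the move from the t-test to a rank test. Secondary outcomes are tested at 0.008, from 0.05/6.

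The preceding paragraph of the same section defines the primary endpoint as the mean baseline-to-10-week difference on the WHYMPI-Interference Scale and names t-tests for it.

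Outcome Measures gives retest figures for three of the instruments:
- WHYMPI-Interference: "stability (0.85 over 2 weeks"
- POMS: "test-retest reliability (0.65 to 0.74, depending on subscale"
- BDI: "stability (.80-.90"

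One of the six secondary outcomes, "Behavioral Goal Adherence", has no baseline entry in Table 4 and "will be assessed via telephone on a weekly basis for 10 weeks post-baseline". No before-and-after test can apply to it.

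**The concern.** The sentence contradicts itself. An analog of a paired t-test must be a paired test, yet the only one named is unpaired. The rank test that corresponds to the paired t-test is the Wilcoxon signed-rank test. With a single arm, there is no between-group comparison for which Mann-Whitney could have been meant.

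An analyst who follows the named example discards the pairing, which is the main statistical advantage of a one-arm before-and-after design with 55 people. When the two scores are positively correlated, an unpaired test uses too large a standard error. It then rejects less often than its nominal level and can miss real improvement. The plan intends to use secondary results to decide which modules to strengthen, so a missed improvement in, say, fatigue or depression could point that work in the wrong direction.

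**Working it through.** The documents give no SD, 10-week correlation, power figure or sidedness, so there is no figure of the plan's own to reproduce. The check asks how the two rank tests behave on paired data of this size.

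**Inputs from the documents.** n = 55; alpha 0.05, and 0.05/6 = 0.0083 for secondary outcomes. The meaningful change on the primary measure is stated as "A reduction in WHYMPI-Interference Scale scores of 0.6 or greater". The retest figures are those listed above.

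**Assumptions.** Two-sided tests; 55 complete pairs; 10-week correlation ρ of 0, 0.3, 0.5 or 0.7; change δ of 0.4 SD. The 0.6-point threshold equals 0.6/1.5 = 0.4 SD if the SD is 1.5, and 0.6/1.0 = 0.6 SD if the SD is 1.0.

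**Step 1: size by normal approximation.** An unpaired analysis takes the standard error of the mean difference to be σ√(2/n). For paired scores it is σ√(2(1−ρ)/n), smaller by the factor √(1−ρ). The actual two-sided size is therefore about 2[1 − Φ(z/√(1−ρ))]. At alpha 0.05, z = 1.96:
- ρ = 0.3: 1.96/0.837 = 2.343, size 1.9%
- ρ = 0.5: 1.96/0.707 = 2.772, size 0.56%
- ρ = 0.7: 1.96/0.548 = 3.578, size 0.03%

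**Step 2: simulation of the tests themselves.** Bivariate normal scores, n = 55, 20,000 data sets per cell (Monte Carlo standard error at most 0.4 points). MW is Mann-Whitney and SR is signed-rank.

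| ρ | Size at 0.05, MW | Size at 0.05, SR | Power at 0.4 SD, alpha 0.05, MW v SR | Power at 0.4 SD, alpha 0.05/6, MW v SR |
|---|---|---|---|---|
| 0 | 5.0% | about 5% | 53 v 52% | 26 v 25% |
| 0.3 | 2.0% | about 5% | 53 v 68% | 23 v 39% |
| 0.5 | 0.6% | about 5% | 54 v 82% | 19 v 56% |
| 0.7 | 0.1% | about 5% | 55 v 96% | 15 v 83% |

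There is no loss at ρ = 0. The simulated sizes agree with Step 1 to within about 0.1 percentage points.

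**Step 3: why Mann-Whitney's own power is flat in one column and falls in the other.** The unpaired statistic has mean about δ√(n/2) and standard deviation √(1−ρ), so its power is about Φ((δ√(n/2) − z)/√(1−ρ)). With √(55/2) = 5.244:
- δ = 0.4 gives 2.10, just above 1.96. At alpha 0.05, raising ρ hardly moves the power.
- The same 2.10 is below 2.638, the critical value at 0.05/6, so there the power falls as ρ rises.
- δ = 0.3 gives 1.57, below 1.96, so the power falls even at alpha 0.05. The simulation gives about 33% at ρ = 0 and 23% at ρ = 0.7, while signed-rank reaches about 79% at ρ = 0.7.

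**Step 4: skewed, floor-bounded scores.** Gamma margins (mean 12, SD 9.8) rounded and clipped to 0–63; mean change about 0.4 SD; alpha 0.05; MW v SR.

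| ρ | Constant shift, clipped at the floor | Proportional reduction |
|---|---|---|
| 0.3 | 79 v 72% | 64 v 79% |
| 0.5 | 82 v 84% | 65 v 90% |
| 0.7 | 87 v 96% | 70 v 99% |

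In one cell Mann-Whitney is ahead. Even on this scale its size with no change is only 2.0%, 0.8% and 0.1% at the three correlations, so it still does not hold its nominal level.

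**The case against.** The best defence is that this is a slip in a test name and not a decision to ignore pairing. The operative method is the paired t-test, the fallback is described as its analog, and Mann-Whitney is only an example. An analyst could use signed-rank without departing from the plan. That stands, and it makes the consequence conditional on two steps. It does not make the sentence right, because the only concrete rank test offered is the wrong one.

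The stakes are also modest. The plan uses the secondary results to modify the program and generate hypotheses, and leaves efficacy to a later randomized trial. No go/no-go rule depends on this test.

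A reader might infer more than the documents support:
- *That the primary analysis is unpaired or invalid.* The sentence does cover the primary hypothesis, but the plan names t-tests for that mean-difference endpoint. The fallback may never be needed there.
- *That false positives are inflated.* This would need negative correlation: at ρ = −0.3 the simulated size is 8.3%. Every retest figure quoted is positive.
- *That a paired test always wins.* It does not at zero correlation, nor in the clipped-shift case at ρ = 0.3. Skew is also when a rank test is most likely to be used.
- *That the retest figures give the 10-week correlation.* They are reliability values, and the WHYMPI figure spans 2 weeks. They make a positive correlation plausible but do not fix its size.
- *That all six secondary outcomes are affected.* At most five have a baseline to compare with.

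**Conclusion.** The plan is wrong as written: the named example does not fit the one-arm paired design, and nothing elsewhere in the document corrects it. The practical effect is limited to the case where the fallback is used and the example is followed, mainly for pain intensity, mood, depressive symptoms, fatigue and sleep.

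In that case the cost is lost power, and it can be large at the Bonferroni level. For a 0.4 SD change with 10-week correlation 0.3 to 0.7, the shortfall against signed-rank is about 16 to 68 percentage points (39 − 23 and 83 − 15). These sizes rest on assumed normal scores, 55 complete pairs, two-sided tests, and correlations and an effect size that the documents do not give. Under skew, the size and even the direction of the difference depend on how improvement occurs. The text should be corrected, but the error does not undermine the trial.

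**What to change.** In the Phase II analytic plan, replace the Mann-Whitney test with the Wilcoxon signed-rank test on the within-participant differences. Add that this test concerns the location of the paired differences, and can be read as a test of their median only if they are roughly symmetric. The present reference to comparing mean or median scores would then agree with what is tested.

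The cost is a few words. Design, sample size and data collection do not change.

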The primary aim of this phase of the project is to execute a pilot feasibility trial to evaluate the preliminary efficacy of, usability of, and satisfaction with the VPMRC.

The primary hypothesis is that a clinically meaningful reduction in pain interference with functioning post-exposure to the VPMRC will be observed compared to baseline ratings.

The secondary hypothesis is that Veterans who participate in the VPMRC will report a clinically meaningful reduction in pain intensity and statistically significant improvements on other important

problems commonly associated with CLBP including fatigue, sleep problems, depressive symptoms and negative mood, relative to baseline.

The tertiary hypothesis is that participants will report high levels of interest (credibility), use, and satisfaction with the VPMRC.

3. Background:

Limitations of current interventions for CLBP

For years, the practice of pain medicine has over-emphasized expensive and modestly effective treatments for CLBP, while under-utilizing inexpensive evidence-based behaviorally-oriented approaches that have demonstrated comparable or superior effect.^{1,2,3,4,5} Non-pharmacological treatments such as education, exercise, and behaviorally-based therapies have been demonstrated to be efficacious and effective, but are rarely used in routine clinical practice. Optimal care should combine both pharmacological and non-pharmacological behavioral interventions – but again, this is rarely done. Patients have historically considered behavioral interventions to be “mental health” resulting in reluctance to accept the need for a “psychological” treatment for their pain. It is imperative that a viable delivery platform be developed to facilitate Veteran access to efficacious non-pharmacological interventions. Such integrated delivery has become the “gold standard” of care for other chronic medical conditions such as diabetes, congestive heart failure, and asthma. The development of the Veterans Pain Management Resource Center (VPMRC) represents a necessary “first step” in providing comparable evidence-based disease management for CLBP – a long anticipated transformation in how clinical pain medicine is practiced.

Behavioral interventions for pain self-management

Cognitive-behavioral therapy

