
We also will post the already approved flyer in the following venues: 1) patient care waiting areas, 2) flat screen informational televisions around the hospital, 3) Good Morning VA Connecticut 4) VA Connecticut's Facebook page, 5) vet centers (after securing their permission) and 6) at the Pain Education table. We also will provide advertisement language in "The Prime Times", a PRIME Center community newsletter.

Procedures

Veterans meeting eligibility criteria based on screening (e.g., by phone) will be scheduled to meet in person with the RA to obtain written informed consent and to complete all baseline study measures. Immediately upon completing the measures, the participant will meet separately with the study coordinator to receive instructions for accessing the VPMRC, and additional logistical details related to their participation in the study. Participants will be provided with a userID and temporary password for accessing the VPMRC program.

Questionnaires and inventories that comprise the principle outcome measures will be reassessed at 10 weeks post-baseline, online using a secure, encrypted Internet-based interface called TrialDB. TrialDB allows participants to complete the self-report questionnaires via their home computer without the need to travel to VACHS. This system has been successfully used to collect data in the HSR&D funded "Women Veterans Cohort Study" (WVCS; PI: [name]). The RA and TrialDB data manager will check the TrialDB reports for accurate and timely completion. The RA will contact participants by phone or email at 10 weeks post-baseline to prompt them to complete post-baseline measures online. If participants are unable to complete the assessments online using TrialDB, alternative arrangements for data collection will be made, such as administering the measures to the participant in person or mailing the measures to the participant with a postage-paid return envelope. The 10 weeks post-baseline timeframe was chosen to allow sufficient time to complete the tailored skills modules and will serve as the post-intervention assessment. Table 4 outlines specific assessment measures to be collected at each assessment point. Participants will be paid \$75 for their participation in each of the two assessments.

Table 4. Phase II Assessment Schedule

	Baseline in-person	Weekly Telephone	10 weeks Post- baseline TrialDB
Regular computer/Internet access	X		
Readiness to Change Checklist	X		

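### The secondary level of 0.05/6 appears to count Behavioral Goal Adherence, which has no baseline value; if each other instrument gives one score, five tests remain and 0.008 is slightly too strict

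*Combined protocol and SAP*

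**What the plan says.** The Analytic Plan for Phase II compares outcomes across time with paired t-tests or non-parametric analogs. For the secondary outcomes it applies a Bonferroni level: "Given the multiplicity of tests for secondary outcomes (i.e., six outcomes) and the power of the study" lead to 0.05/6, given as 0.008. The six are not named there. The plan adds that it did not group outcomes into subsets and calls this the more conservative choice.

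The other relevant places are:

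- **Purpose, secondary hypothesis.** Veterans are predicted to "report a clinically meaningful reduction in pain intensity and statistically significant improvements on other important" complaints, which the hypothesis then lists as "problems commonly associated with CLBP including fatigue, sleep problems, depressive symptoms and negative mood, relative to baseline". This names five constructs. Goal adherence is not one of them.
- **Outcome Measures, Secondary Outcomes.** There are five headings. Emotional functioning covers two instruments (POMS and BDI), so the section holds six measures: NRS, POMS, BDI, MFI, MOS Sleep and Behavioral Goal Adherence.
- **Phase II, Design.** A single condition with "two evaluation periods (baseline and 10 weeks post-baseline) design with multiple dependent measures will be employed".
- **Table 4.** Goal adherence is marked at the weekly telephone contacts and at week 10, not at baseline. The other five instruments are marked at baseline and week 10.
- **Procedures.** Access follows the baseline assessment: "Immediately upon completing the measures, the participant will meet separately with the study coordinator to receive instructions for accessing the VPMRC". The calls come later: "participants will be contacted by the study staff via telephone on a weekly basis beginning 1 week post-baseline and ending at 10 weeks post-baseline".
- **Behavioral Goal Adherence.** The section says that "goals will be assessed via telephone on a weekly basis for 10 weeks post-baseline", with each rating referring to the week before the call.

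**The concern.** A Bonferroni divisor should equal the number of tests that will be run. Here six matches the list of measures only if one of them is goal adherence. That measure rates adherence to goals set inside the program, and participants receive access instructions only after completing the baseline measures. A baseline value is therefore not just unscheduled; there is nothing yet to rate. The planned paired test against baseline cannot be run on it.

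Two things are at stake. First, a divisor that is too large gives up some power in a 55-person pilot whose secondary results help decide which modules are revised. Second, because neither the six outcomes nor the score used from each multi-scale instrument is written down, the tested family can still be settled after the data are seen.

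**Working it through.** **1. The plan's own figure.** 0.05/6 = 0.00833, which is 0.008 to three decimals. It is reproduced; the rounding is downward and so conservative.

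**2. Which measures allow a baseline-to-week-10 test (Table 4).**

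| Measure | Baseline | Week 10 | Scores described | Single test score named? |
|---|---|---|---|---|
| NRS | yes | yes | 1 | yes |
| POMS | yes | yes | 6 dimensions | no |
| BDI | yes | yes | 1 | yes |
| MFI | yes | yes | 5 dimensions | no |
| MOS Sleep | yes | yes | 7 domains plus 1 item | no |
| Goal adherence | no | yes | 1 | not applicable |

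Five measures qualify if each supplies one score.

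**3. Family-wise error.** The bound is (number of tests) × (level per test).

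- Five tests at 0.008: 5 × 0.008 = 0.040. Simulated with all five null and n = 55, the error is 3.9%, 3.8% and 3.1% at assumed correlations of 0, 0.3 and 0.6.
- Four tests, if NRS is judged only by its 30% criterion: 4 × 0.008 = 0.032.
- Every listed score: 1 + 6 + 1 + 5 + 7 = 20, or 21 with the sleep-quantity item. 20 × 0.008 = 0.160 and 21 × 0.008 = 0.168.

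**4. Power cost of the divisor.** Two-sided paired t-test, noncentral t with n − 1 degrees of freedom and noncentrality d√n. The documents give no standardized change d, so 0.3 to 0.5 is assumed. The plan does not state sidedness; two-sided is assumed. The 44 completers assume 20% loss (55 × 0.8).

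| n | d | at 0.008 | at 0.05/6 | at 0.05/5 |
|---|---|---|---|---|
| 55 | 0.3 | 30.9% | 31.4% | 33.8% |
| 55 | 0.4 | 58.6% | 59.2% | 61.8% |
| 55 | 0.5 | 82.5% | 82.9% | 84.6% |
| 44 | 0.4 | 45.7% | 46.3% | 49.0% |

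At n = 55 and d = 0.4 the divisor alone accounts for 61.8 − 59.2 = 2.6 points, or 61.8 − 58.6 = 3.2 points against the rounded 0.008. With a family of four, 0.05/4 gives 64.9%.

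**5. Holm, shown separately because it is a change of method.** Simulated over five measures with n = 55, d = 0.4 and correlation 0.3, the power per truly changed measure is about 62%, 63%, 66%, 69% and 73% when one, two, three, four or all five change. Family-wise error stayed below 5% in every configuration run. If all five change, the gain over 0.05/6 is 73 − 59 = 14 points. Correcting the divisor first gives about 3 of these and Holm about 11. Taken in the other order, Holm with six left in the family already reaches about 67% (8 points), and the divisor adds about 6. Holm supplies most of the gain either way.

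**The case against.** The case for leaving the plan alone has four parts.

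- **The six are unlisted.** Attributing the sixth to goal adherence is an inference, and the plan's count does agree with its own list of measures. This stands, and is why the heading says that it appears to be counted.
- **A week-1 to week-10 contrast would be a comparison across time.** This is true, and six would then be right. But no such contrast is specified, the hypothesis is relative to baseline, and the design has two evaluation periods.
- **Too large a divisor still controls error, and the plan says it chose to be conservative.** This also stands. The divisor makes no test invalid; it gives up a little power.
- **Preferring Holm to a valid Bonferroni is a choice of method.** This is fair, so its gain should not be charged to the miscount. Holm does have the same error control and never less power.

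Two stronger readings are tempting. A reader might infer that the family is definitely five and that error is therefore definitely not inflated. The documents do not settle this: no total or lead score is named for MFI or MOS Sleep, and the phrase "Overall functioning will be assessed using the 65-item Profile of Mood States (POMS") may hint at a POMS total but names none. Conversely, a reader might take the remark about not grouping into subsets to mean that every subscale will be tested at 0.008, with error near 16%. The remark is ambiguous, and a stated count of six fits instruments better than 20 or 21 subscale scores. Neither reading can be asserted from the text.

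**Conclusion.** The point holds in conditional form and is minor. The stated divisor does not match the set of measures that can receive the planned baseline-to-week-10 test. With one score per instrument that set has five members, 0.008 is slightly too strict, and the family-wise bound is 4.0%, below the nominal 5%. The direction would reverse only if subscale scores were tested individually at 0.008.

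The cost of about 3 points rests on the assumed d = 0.4 with n = 55; across d = 0.3 to 0.5 it is about 2 to 3 points. The simulated figures also rest on assumed correlations. The plan describes the secondary outcomes as informing program changes and generating hypotheses, and leaves efficacy to a later randomized trial. Its one example of revising modules from outcome data turns on the size of change, not on a 0.008 threshold, so the practical effect of the lost power is limited. The more useful gain is that the tested family would be fixed before data are seen. Confidence is medium because the six outcomes are not named.

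**What to change.** In the Phase II Analytic Plan:

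1. List the secondary outcomes that will be tested.
2. Summarise the weekly course of Behavioral Goal Adherence descriptively. If a week-1 to week-10 test is intended, say so and keep six.
3. Before data are seen, name the one POMS, one MFI and one MOS Sleep score that each test uses.
4. State whether NRS has a significance test or is judged only by its 30% criterion, and match the divisor to the final list.
5. Apply Holm across that list at overall 0.05 in place of Bonferroni.
6. Report the remaining subscales with confidence intervals only.

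Items 1 to 4 are the essential repair; item 5 is an improvement in method. The cost is wording only, with no new data or visits. The downside is that goal adherence and the other subscales have no formal test.
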